Inhibitory Control Task: Inhibitory control was assessed using a letter version of the Eriksen flanker task (Eriksen & Eriksen, 1974; McGowan et al., 2019), which is classified as a behavioral response selection construct of the inhibition/suppression focus and the performance monitoring focus of cognitive control according to the NIMH Research Domain Criteria (RDoC) classification system. Participants were instructed to attend to and to respond as accurately as possible to a centrally presented stimulus nested amid either congruous ('MMMMM') or incongruous ('NNMNN') flanking stimuli. Participants completed 80 practice trials at pretest followed by 160 trials grouped into two blocks of 80 trials, each consisting of equiprobable congruency and directionality; at each assessment period (160 trials pre-experimental condition and 160 trials post-experimental condition). For each block of trials, participants were presented with perceptually similar letter pairs (e.g., pretest block 1: M – N, pretest block 2: E – F, posttest block 1: I – T, posttest block 2: U – V) and were instructed to respond by pressing the button assigned to the letter presented in the middle of the flanking letters.

To ensure a high degree of task difficulty, at the midpoint of each block participants were given instructions to reverse the button-letter assignments (e.g., left button press for “M” through the first 40 trials and then right button press for “M” through the last 40 trials). Flanking letters were presented 300 ms prior to the onset of the target letter, and all five letters remained on the screen for a subsequent 100 ms (for a total stimulus duration of 400 ms) with a response window of 1000 ms and a variable inter-trial interval of 2300, 2400, 2500, 2600, or 2700 ms. All stimuli were 1.5 cm tall white block letters presented focally on a black background. Stimulus presentation and timing were controlled using PsychoPy 1.86 (Peirce, 2009). Reaction time was quantified within each congruency as the mean speed of responding following the onset of the stimulus only for correct trials. Response accuracy was quantified within each congruency as the proportion of correct responses relative to the number of trials administered.

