Sustained Attention Task: Sustained attention was assessed using the rapid visual information processing task (Chandler et al., 2020; Neale et al., 2015) which is classified as a behavioral construct of attention according to the NIMH Research Domain Criteria (RDoC) classification system. Participants were presented with a series of single digits (1-9) in a box in the center of the screen at a rate of 100 digits/min and were instructed to make a button response with their right thumb as soon as they detected any of the three target sequences: ‘2-4-6,’ ‘3-5-7,’ or ‘4-6-8.’ To minimize working memory load, the three target sequences were presented on the bottom of the screen throughout the duration of the task. At pretest, participants completed a 1 min practice period prior to beginning the test trials which contained a series of 402 digits with 64 target sequences embedded. At posttest, participants completed another series of 402 digits with 64 target sequences embedded. Reaction time was quantified as the mean speed of responding following the presentation of the final digit of the target sequences only for correct sequence identifications. Response accuracy was quantified as the proportion of responses that correctly coincided with the 64 target sequences presented.

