Following removal of the eye blink components, stimulus-locked epochs were created for correct trials from -500 to 1,500 ms around the stimulus, baseline corrected using the -100 to 0 ms pre-stimulus period, and filtered using a zero phase shift low-pass filter at 30 Hz. Trials with artifact exceeding $\pm 100 \mu\text{V}$ were rejected. To ensure the integrity of the signal, stimulus-locked epochs were visually inspected blind to the experimental condition and dose prior to computing mean waveforms. Following visual inspection, the mean number of trials included in the waveforms was 112.0 [95% CI: 107.2 to 116.7] trials stimulus-locked to the congruent and incongruent trials (separately) of the Inhibitory Control task and 41.6 [95% CI: 40.1 to 43.2] trials stimulus-locked to the final stimulus of the target sequences of the Sustained Attention task.

Attention was indexed by the P3 ERP component. Attentional engagement was evaluated as the mean amplitude within a 50 ms interval surrounding the largest positive going peak within a 275 to 700 ms latency window following stimulus onset for the flanker task, and a 275 to 600 ms window for the RVIP task (Chandler et al., 2020; McGowan et al., 2019; Pontifex et al., 2015). Attentional processing speed was evaluated using ERP latency which was quantified as the time at which maximum peak amplitude occurred. Given the well-established nature of the P3 ERP component, analyses were conducted using a nine-channel region-of-interest approach centering around the topographic maxima of the P3 (i.e., the CP3/Z/4, P3/Z/4, PO5/Z/6 electrodes).

Aims Assessment:

- 1) *To provide a preliminary assessment of the safety profile of combining intranasal insulin with exercise; to ensure that undue risks are not incurred through combination therapeutic approaches.*

As the present investigation was a Phase II Clinical Trial, the research design is not sufficiently powered for hypothesis testing. Accordingly, this aim was satisfied by:

- A) Examining the frequency of participants reporting potential side effects of intranasal insulin at any time during the experimental protocol.
 - B) Examining the frequency of participants reporting potential side effects of intranasal insulin that persisted at the end of the experimental protocol.

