 - C) Examining the frequency of study discontinuations due to violations of the safety thresholds (e.g., blood glucose outside the range of 70 to 150 mg/dL, feeling dizzy, or unable to safety continue the experimental protocol).
- 2) *To provide a preliminary assessment of the efficacy of combining intranasal insulin with exercise for enhancing inhibitory aspects of cognitive control and sustained attention alongside neuroelectric indices of attention.*

As the present investigation was a Phase II Clinical Trial, the research design is not sufficiently powered for hypothesis testing. Accordingly, this aim was satisfied by computing the within subject effect size for each participant as the standardized change relative to the pretest assessment using the within-subject (d_{rm}) variance correction for Cohen's d (Lakens, 2013). To ensure the integrity of the effect size estimates, within-subject effect sizes exceeding 3 times the interquartile range were identified as outliers and removed from analysis. For each measure, within each experimental condition, the effect of intranasal insulin was corrected by subtracting the effect size observed for the 0 IU placebo group to isolate the effects of intranasal insulin. Preliminary assessments of the efficacy were thus quantified using:

- A) Effect size estimates with 95% confidence intervals for both control and exercise conditions collapsed across congruencies of the Flanker task to quantify the effects on **Behavioral Indices of Inhibitory Control**. Reaction time effects and response accuracy effects were separately extracted.
- B) Effect size estimates with 95% confidence intervals for both control and exercise conditions in response to the target trial of the Rapid Visual Information Processing task to quantify the effects on **Behavioral Indices of Sustained Attention**. Reaction time effects and response accuracy effects were separately extracted.

- C) Effect size estimates with 95% confidence intervals for both control and exercise conditions for P3 amplitude at the nine-channel region-of-interest to quantify the effects on **Neuroelectric Indices of Attentional Engagement**. Effects collapsed across congruencies of the Flanker task and effects for the target trial of the Rapid Visual Information Processing task were separately extracted.

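### RVIP response accuracy is a one-sided score with an unclear denominator, so a shift in response criterion can move it in either direction with no change in sensitivity.

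*Combined protocol and SAP*

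**What the plan says.** All references are to the combined protocol and SAP.

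- **Measures, Sustained Attention Task.** Digits appear "at a rate of 100 digits/min". The pretest has 402 digits containing 64 targets, and the posttest has "another series of 402 digits with 64 target sequences embedded". Accuracy is defined as follows: "Response accuracy was quantified as the proportion of responses that correctly coincided with the 64 target sequences presented". Reaction time is taken "only for correct sequence identifications". No response window is given.
- **Measures, Inhibitory Control Task.** Flanker accuracy has an explicit denominator: "the proportion of correct responses relative to the number of trials administered". That task also has a stated 1000 ms response window.
- **Measures, Neuroelectric Indices of Attention.** "stimulus-locked epochs were created for correct trials", and the mean number retained for the RVIP was "41.6 [95% CI: 40.1 to 43.2] trials stimulus-locked to the final stimulus of the target sequences".
- **Aims Assessment, Aim 2, item B.** Effect sizes for the target trial are used "to quantify the effects on Behavioral Indices of Sustained Attention". Only reaction time and response accuracy are extracted. Each effect is corrected, within the exercise or the control condition, by subtracting the effect size of the 0 IU group.

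No false-alarm rate, d-prime, A-prime or other sensitivity index appears anywhere in the document.

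**The concern.** The RVIP is a free-response task. The participant may press at any digit, and most digits do not complete a target. Two things govern performance: how well targets are told apart from other digits (sensitivity), and how readily the participant presses (criterion). A score that uses only hits, or only the fraction of presses that were hits, mixes the two.

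Taken literally, the accuracy sentence makes presses the denominator. The mention of the 64 targets, the reference to the target trial in Aim 2 item B and the parallel with the flanker definition all point to hits/64 instead. Hits/64 is the likelier intention, but the text does not settle it.

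The rest of the plan does not fill the gap. RVIP reaction time and the P3 measures use correct trials only, so false alarms enter neither. Accuracy is one of two behavioural indices from which Aim 2 speaks about sustained attention. A reader cannot tell from the plan which quantity was computed, or whether a change in it reflects attention or willingness to press.

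**Working it through.** The plan states no RVIP accuracy value, false-alarm count or sample size, so there is no figure to reproduce. The check asks how far each candidate score moves when sensitivity is fixed and only the criterion changes.

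**Inputs from the documents**
- 402 digits and 64 targets per assessment, so 402 − 64 = 338 digits do not complete a target.
- 100 digits per minute, so 60,000/100 = 600 ms per digit.
- Mean retained correct-trial RVIP epochs 41.6, and 41.6/64 = 0.65.

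**Assumptions**
- Baseline hit rate 0.65. Retained epochs are counted after artifact rejection, so 0.65 is a lower bound on the mean hit rate if the count is per assessment, which the text does not say. I therefore also show 0.50 and 0.80.
- d-prime 2.5, with 2.0 and 3.0 as the range.
- Equal-variance signal-detection model, with each digit one opportunity to respond.

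**Formulas.** With Φ the normal distribution function, z its inverse and c the criterion:
- hit rate H = Φ(d′ − c)
- false-alarm rate F = Φ(−c)
- baseline c = d′ − z(H)
- reading A (hits/64) = H
- reading B (hits/responses) = 64H/(64H + 338F)

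**Step 1: d′ = 2.5, baseline H = 0.65.**
- Baseline: c = 2.5 − 0.385 = 2.115, F = 0.0172. Hits 64 × 0.65 = 41.6; false alarms 338 × 0.0172 = 5.8. A = 0.65; B = 41.6/47.4 = 0.88.
- Criterion 0.5 SD more liberal: c = 1.615, H = Φ(0.885) = 0.812, F = 0.0532. Hits 52.0; false alarms 18.0. A = 0.81; B = 52.0/70.0 = 0.74.
- Criterion 0.5 SD stricter: c = 2.615, H = 0.454, F = 0.0045. Hits 29.1; false alarms 1.5. A = 0.45; B = 29.1/30.6 = 0.95.

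d-prime is 2.5 in all three cases. The two readings move in opposite directions each time.

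**Step 2: range, 0.5 SD more liberal criterion.**

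| Baseline H | d′ | hits/64 | hits/responses |
|---|---|---|---|
| 0.65 | 2.0 | 0.65 → 0.81 | 0.70 → 0.54 |
| 0.65 | 2.5 | 0.65 → 0.81 | 0.88 → 0.74 |
| 0.65 | 3.0 | 0.65 → 0.81 | 0.96 → 0.90 |
| 0.50 | 2.5 | 0.50 → 0.69 | 0.94 → 0.85 |
| 0.80 | 2.5 | 0.80 → 0.91 | 0.76 → 0.58 |

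**Step 3: what the placebo correction does.** I use raw proportions, because the plan gives no standard deviations from which to form d_rm. Take reading A and a shift worth 0.812 − 0.650 = 0.162.
- Insulin and 0 IU groups both shift: 0.162 − 0.162 = 0. The artefact cancels.
- Only the insulin group shifts: 0.162 − 0 = 0.162. The artefact stays in full.

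**Step 4: the missing window.** Digits arrive every 600 ms. If the flanker's 1000 ms window were borrowed (an assumption), it would span 1000/600 = 1.67 digits. A press after the next digit could then count as a hit for the target before it. Hits, false alarms and the figure of 338 opportunities all depend on a window that the plan does not state.

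**The case against.** **Pressing more is rewarded.** A reader might infer that a participant who simply presses more is scored as having better sustained attention. The documents support this only under hits/64. Under hits/responses, extra presses lower the score and withholding presses raises it.

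**Exercise cannot be masked.** A reader might also infer that participants who know they exercised become more willing to press, and that this passes for an effect on attention. For the insulin effect the plan largely answers this. The 0 IU exercise group does the same exercise with the same knowledge, and its effect is subtracted within the condition, so on average the shared part cancels. What remains is a shift caused by insulin dose, alone or combined with exercise, and dose is described as double-blind.

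**Context resolves the denominator.** The pointers to hits/64 are good, so the opposite-sign result rests on the less likely reading. That makes the ambiguity modest, but choosing hits/64 still leaves false alarms uncounted.

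**The size is hypothetical.** This stands. No false-alarm data are given, so the real bias is unknown.

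**A new index would switch the outcome after the fact.** This also stands against replacement. The document is written in the past tense and already reports observed heart rates and epoch counts. Nor is d-prime wholly free of bias in a free-response stream: it depends on the window and on the equal-variance assumption. Both points argue for a supplementary analysis.

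**Limited reach.** RVIP accuracy is one of several Aim 2 measures, and the plan disclaims hypothesis testing. Safety Aim 1 is untouched.

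**Conclusion.** The concern holds in a limited form. RVIP accuracy is a single proportion whose denominator is unclear and which omits one type of error under either reading, and nothing else in the plan supplies the omitted part. At fixed sensitivity, a 0.5 SD criterion shift is enough to move hits/64 by about 0.16 from an assumed baseline of 0.65 (by 0.11 to 0.19 over baselines of 0.80 to 0.50). At the 0.65 baseline it moves hits/responses by about 0.07 to 0.16 the other way, for d-prime from 3.0 to 2.0. These figures show what is possible under the stated model; they do not estimate bias in this trial.

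The documents do not show that any such shift occurred, that it favours frequent pressing in particular, or that unmasked exercise distorts the placebo-corrected effects. The exposure that remains is a criterion shift that differs between an insulin dose and 0 IU within a condition. This is worth correcting because it is cheap. It bears on how one exploratory measure is interpreted, and not on the trial's other results.

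**What to change.** 1. State that RVIP accuracy is hits divided by 64, and give the response window that makes a press a hit. Say how a press falling after the next digit is classified, since digits are 600 ms apart.
2. Report the number of false alarms beside the hit rate, by dose, condition and assessment.
3. Add a sensitivity index from the same button-press log as a supplementary analysis: A-prime, or d-prime with the log-linear correction. If all 338 other digits count as opportunities, d′ = z((hits + 0.5)/65) − z((false alarms + 0.5)/339). Adjust the 339 if the window removes some digits. Pass the index through the same effect-size and 0 IU subtraction steps.
4. Keep the specified accuracy score, and label the index as added after data collection. Describe a change in accuracy as a change in sustained attention only if the index agrees.

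**Cost.** One derived variable and an extra column or two in the results, with no new data collection. The index depends on the chosen window, so repeating it with a second plausible window would be sensible. It also requires that every press was logged, which the documents do not state. If only correct presses were kept, the index cannot be computed, and the report should say that accuracy was not separated from response criterion.

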Study Protocol and Statistical Analysis Plan
For Research Project:
“Safety and Efficacy of Combining Intranasal Insulin & Acute Exercise”

clinicaltrials.gov # NCT04292535

conducted by [name], Ph.D.

March 19, 2021

“Safety and Efficacy of Combining Intranasal Insulin & Acute Exercise”

Abstract: To determine if physical activity engagement alters the dose-response profile and safety of administration of insulin into the intranasal mucosa. Using a randomized placebo controlled double-blind pre-posttest design, participants were randomly assigned to receive a dose of either 0, 20, 40, 60, 80, 100, or 120 IU of NovoLog insulin aspart prior to being randomized into participating in a 20 minute session of either moderate-intensity aerobic exercise or a passive control condition. The safety of the protocol was assessed using a symptom questionnaire assessing common symptoms of altered blood glucose and common side effects of intranasal insulin. The efficacy of the intranasal insulin for inducing alterations in cognition was assessed using both behavioral and neuroelectric measures.

Aims:

- 1) To provide a preliminary assessment of the safety profile of combining intranasal insulin with exercise; to ensure that undue risks are not incurred through combination therapeutic approaches.
- 2) To provide a preliminary assessment of the efficacy of combining intranasal insulin with exercise for enhancing inhibitory aspects of cognitive control and sustained attention alongside neuroelectric indices of attention.

Design: Double blind, placebo controlled Phase 2 clinical trial using serial stratification randomization accounting for biological sex. Participants were first allocated to a dose of intranasal insulin (0 [placebo], 20, 40, 60, 80, 100, 120 IU), then allocated to either exercise or control activity.

Study Population: Given the potential risk of combining exercise with intranasal insulin the present investigation utilized a sample of healthy, non-diabetic, fasted college-aged adults to limit the potential for a serious adverse event. The sample consisted of college aged young adults from the mid-Michigan, USA area.

Eligibility Criteria:

Criteria for inclusion: All individuals that agreed to participate were selected on a first come, first serve basis. No individual was turned down due to sex, race, or ethnicity. The following inclusion criteria exist for all participants:

- a. Participants must be over the age of 18.

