- b. Participants must have normal or corrected-to-normal vision in order to complete the cognitive task.

Exclusion criteria: The following exclusion criteria exist for all participants:

- a. Lack of consent.
- b. Presence of any major neurological health issues, brain trauma, or concussion with loss of consciousness assessed through a health history and demographics questionnaire.
- c. Type I or Type II Diabetes.
- d. Self-reported pregnancy.
- e. Currently has any type of inflammation or blockage of the nasal passageways (i.e. allergies or a cold affecting the sinuses).
- f. Inability to engage in treadmill-based exercise.

Recruitment: Participants were recruited from the mid-Michigan community population via flyers and list-serve announcements.

Protocol: This investigation was approved by the Michigan State University Human Research Protection Program.

Screening Day (day 1): On the screening day of the testing protocol, following consenting to participate in this investigation; participants completed a brief health and history demographics questionnaire, a physical activity readiness questionnaire (Thomas et al., 1992), a medical screening questionnaire, the Wechsler Abbreviated Scale of Intelligence – 2nd Edition (WASI-II; (Wechsler, 2011), and a test of maximal oxygen uptake ($VO_2\text{max}$; using the same protocols as reported in (Chandler et al., 2019; Pontifex et al., 2016)). The medical screening questionnaire ensured that all participants were free of medication for high blood pressure, cholesterol, asthma, heart issues, depression/anxiety; and were not currently on any beta-blockers, sulfonamide antibiotics, corticosteroids, protease inhibitors, or Clonidine.

Participants who were eligible to continue in the study were then randomly assigned using a serial stratification approach accounting for biological sex to either an exercise [active experimental group] condition or sitting [control experimental group] condition. Within each condition; participants were subsequently randomly assigned using a serial stratification approach accounting for biological sex to receive a dose of either 0, 20, 40, 60, 80, 100, or 120 IU of fast acting insulin (Novolog Insulin Aspart 100 mg/mL) administered into the intranasal mucosa. Participants were instructed to refrain from exercise or caffeine intake, and too fast for at least 3 hours prior to participating in the second day of the testing protocol.

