Assessment day (day 2): See Figure 1 for an overview of the assessment activities.

[figure not shown]

Figure 1. Diagram of experimental protocol.

Upon arriving to start the second day of testing, participants' blood glucose level was assessed via a glucometer (CVS Health Advanced Blood Glucose Meter, United States) to ensure that their blood glucose fell within the 70-115 mg/dL guideline to exercise safely. Following this, participants were outfitted with a polar heart rate monitor (Model H7, Polar Electro, Finland) to assess heart rate during the experimental condition and then were prepared for neuroelectric testing. Participants were subsequently seated in a sound-attenuated testing chamber approximately 1 m away from the computer monitor where they completed tests of inhibitory control and sustained attention while behavioral and neuroelectric measures were assessed. Once the pretest cognitive assessment was completed, participants were administered solution into their intranasal mucosa.

Using a double-blind, placebo-controlled approach; identical vials of saline solution and Novolog insulin aspart 100 mg/mL were obtained differentiated only by the color of the stopper top, and labeled as investigational drug A and investigational drug B. All participants were administered 6 doses of 0.2 mL of solution via the LMA MAD Nasal Intranasal Mucosal Atomization device into alternating nostrils with a total administration volume of 1.2 mL. The dose of intranasal insulin was controlled by varying the number of doses which contained saline relative to the doses which contained Novolog insulin aspart 100 mg/mL (see Figure 2). The experimenters were aware of the number of doses of investigational drug A and investigational drug B administered; but were unaware which solution or stopper top was associated with insulin or saline. Following administration of the solution, participants completed the sitting/exercise experimental conditions.

Figure 2. Illustration of the intranasal insulin dosing protocol.

Active Comparator: Passive Control. The sitting experimental condition consisted of a 20 min duration where participants sat in a chair (HR = 73.2 bpm [95% CI: 70.3 to 76.2]).

Intervention. The exercise experimental condition consisted of similar 20 min duration of exercise on a motor-driven treadmill at an intensity between 60 and 65% of maximum heart rate achieved during the test of maximal oxygen uptake (HR = 118.1 bpm [95% CI: 116.2 to 120.1]).

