During both the sitting and exercise experimental conditions, participants watched an emotionally neutral video (minutes 65-85 from Wonders of the Universe (*Wonders of the Universe*, 2011)). Midway through the sitting and exercise experimental conditions and again 5 minutes following the completion of the experimental conditions, peripheral blood glucose was assessed via a glucometer. If peripheral blood glucose fell below 70 mg/dL, testing was immediately discontinued for all measures. Following the peripheral blood glucose assessment, participants again completed the tests of inhibitory control and sustained attention while behavioral and neuroelectric measures were assessed. Finally, upon completion of the cognitive assessments, participants completed a symptom survey which assessed potential side effects of intranasal insulin that participants might have experienced at any time during the experimental protocol and if participants were still experiencing those symptoms.

Measures:

Safety of Intranasal Insulin: The safety of intranasal insulin in combination with exercise was assessed by examining the incidence of participants reporting potential side effects of intranasal insulin (Schmid et al., 2018) at any time during the experimental protocol and the persistence of those symptoms. Additionally, the extent to which peripheral blood glucose was altered was also assessed via glucometer at the beginning of the session, during the middle of the exercise/sitting condition, and following the exercise/sitting condition

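### Aim 1A and 1B are stated as raw symptom frequencies with no comparison to the 0 IU group, so they cannot be read as effects of insulin

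*Combined protocol and SAP*

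**What the plan says.** All references are to the combined protocol and SAP.

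**Analysis.** Aim 1 in the Aims Assessment has three items, all frequencies.
- Item A is "Examining the frequency of participants reporting potential side effects of intranasal insulin at any time during the experimental protocol".
- Item B is the frequency of such side effects still present when the session ended.
- Item C counts discontinuations and is not at issue here.

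None of the three mentions dose, activity or the 0 IU group. Aim 2, in the same section, subtracts the 0 IU effect size within each activity, in order to isolate what insulin does, and gives 95% confidence intervals.

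**Data.** The text on the assessment day describes one symptom survey, given after the posttest tasks. It covers "potential side effects of intranasal insulin that participants might have experienced at any time during the experimental protocol" and asks whether symptoms are still present. The spray comes well into the session: "Once the pretest cognitive assessment was completed, participants were administered solution into their intranasal mucosa". The Abstract calls the instrument a "symptom questionnaire assessing common symptoms of altered blood glucose and common side effects of intranasal insulin".

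**State of participants before the spray.** They were told to "refrain from exercise or caffeine intake, and too fast for at least 3 hours prior to participating in the second day". Two rules limit symptoms on arrival: exclusion criterion e ("Currently has any type of inflammation or blockage of the nasal passageways") and a glucose check "to ensure that their blood glucose fell within the 70-115 mg/dL guideline to exercise safely". Under Measures, blood glucose has a pre-dose reading, as it "was also assessed via glucometer at the beginning of the session". No equivalent is described for symptoms.

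**The concern.** A raw frequency of symptoms labelled as potential side effects invites the reader to attribute all of it to insulin. Here it can mix at least three other sources: ordinary background symptoms, the effects of fasting and caffeine abstention, and, in half of the design, the effects of 20 minutes of treadmill exercise. The literal survey window adds a fourth route, because a symptom that began before any solution was given can be counted.

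Aim 1 asks whether combining insulin with exercise adds undue risk. That question is about excess over what would have occurred without insulin, and a raw frequency does not answer it. The design contains the right comparator, a randomised, blinded 0 IU group within each activity that receives the same six sprays. The plan uses it for Aim 2 and does not commit to using it for Aim 1.

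**Working it through.** The plan gives no symptom rate, sample size or power figure, so there is nothing of its own to reproduce. All rates and cell sizes below are assumptions.

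**1. How much of the session precedes the spray?** Inputs are the task descriptions under Measures and the day 2 timings. I assume that the mean flanker inter-trial interval of 2.5 s runs from onset to onset.
- Before: flanker (80 + 160) × 2.5 s = 600 s = 10 min; sustained attention 402/100 + 1 min practice ≈ 5 min. Total ≈ 15 min, not counting EEG preparation.
- After: 20 min activity + 5 min + flanker 160 × 2.5 s ≈ 6.7 min + sustained attention ≈ 4 min. Total ≈ 36 min.
- Share before the spray: 15/(15 + 36) ≈ 30%. It is somewhat higher if the interval excludes stimulus or response time.

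So if the window was the whole session, its pre-spray part is not negligible.

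**2. Raw frequency against difference from 0 IU.** Let b be the frequency of symptoms from all causes other than insulin, equal in all dose groups of one activity by randomisation, and p the insulin-caused frequency. Assuming independence:
- raw frequency at an active dose: t = 1 − (1 − b)(1 − p)
- difference from 0 IU: t − b = p(1 − b)
- share of reporters with non-insulin symptoms only: b(1 − p)/t

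With p = 10%:

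| b | raw t | t − b | share non-insulin only |
|---|---|---|---|
| 5% | 14.5% | 9.5 points | 31% |
| 10% | 19.0% | 9.0 points | 47% |
| 20% | 28.0% | 8.0 points | 64% |
| 30% | 37.0% | 7.0 points | 73% |

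With p = 0 the raw frequency equals b and the difference is 0. The raw figure follows the background; the difference stays near p, slightly diluted.

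**3. The part due to the survey window alone.** Let p0 be the pre-spray prevalence and p1 the true post-spray frequency from any cause. Under independence the inflation is p0(1 − p1).
- With p1 = 10%: p0 = 2% gives 11.8%, 5% gives 14.5%, 10% gives 19.0%.
- Without independence it lies between max(0, p0 − p1) and p0: 0 to 10 points at p0 = p1 = 10%.
- In participants, at p0 = p1 = 10% and an assumed 5-12 per cell: 5 × 0.10 × 0.90 = 0.45 to 12 × 0.10 × 0.90 = 1.08 extra reporters per cell. Over the six active doses of one activity this is 2.7 to 6.5.

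**4. What the window does to a difference.** Take true frequencies of 30% at an active dose and 10% at 0 IU. Under independence the 20-point difference becomes (1 − p0) × 20: 18 points at p0 = 10%, 16 at 20%, 12 at 40%. With no overlap it stays 20. With complete overlap it is max(p0, 30) − max(p0, 10): 20, 10 and 0 points.

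**5. Precision of the difference.** With 19% against 10%, the approximate 95% half-width is 1.96 × √[(0.19 × 0.81 + 0.10 × 0.90)/n] = 1.96 × √(0.2439/n): about 43 points at n = 5 and 28 points at n = 12. With the six active doses pooled it is 1.96 × √[0.1539/(6n) + 0.09/n]: about 30 and 19 points. The normal approximation is rough at these sizes and serves only to show scale.

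**The case against.** The strongest defence has four parts.

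- **The phrase itself limits the count.** A side effect of the spray cannot precede the spray, and the survey form may have said so. This stands as far as it goes. The form is not in the documents and Figure 1, the session diagram, is not shown, so a reader who infers that pre-spray symptoms were in fact counted goes beyond the evidence. What can be said is that no stated rule prevents it. The items are also unlisted, so which background symptoms would be picked up is unknown.
- **Only 1A uses the any-time window.** This is correct. A reader might take 1B to share it, but 1B counts persistence at the end, and the window reaches it only through a symptom that began earlier and lasted.
- **The design already controls for background.** Dose is randomised with a 0 IU group in each activity, and the Abstract speaks of a dose-response profile, so results by dose may well be shown. This is why the remedy is easy. It is not an answer, because Aim 1 as written commits to no such comparison while Aim 2 does.
- **Over-counting is conservative for safety.** Inflated raw counts do not by themselves hide harm, and a reader should not infer that they do. The severe dilution in step 4 needs a pre-spray prevalence of 40%, for which the documents give no support.

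That Aim 1 is descriptive and unpowered does not remove the point: a descriptive frequency still needs a reference before it can be attributed to insulin.

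**Conclusion.** The point holds in a limited form. As stated, 1A and 1B give raw symptom frequencies without the 0 IU reference that the same document uses for efficacy, and these cannot be read as effects of insulin. The main reason is the missing comparison. The literal survey window is a secondary and unproven contributor.

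The size cannot be determined from the documents. Under the assumed rates in step 2, between about a third and three quarters of reporters at an active dose could have non-insulin symptoms only. The window alone would add about one participant per cell at an assumed 5-12 per cell. The 0 IU difference removes background, fasting and exercise symptoms on average, because randomisation balances them across doses within an activity. It may remain somewhat diluted, and with cells of that size it will be imprecise. This is an improvement to a descriptive safety aim; the documents do not support the claim that the safety results are wrong or that harm is concealed.

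**What to change.** **Change to Aim 1.** Report 1A and 1B by dose within each activity, as the difference from the 0 IU group of the same activity, with a 95% confidence interval from a method suited to small cells. Keep the raw counts in the table beside the difference, since they describe overall tolerability, but do not attribute them to insulin. A pooled active-dose row for each activity would help, given the widths in step 5.

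**Cost.** No new data are needed: it takes a 0 IU column and an interval in the symptom table. The price is wide intervals, which show how little such cells can say about individual doses.

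**Question for the sponsor.** Did the survey ask about the whole session or only the time after the spray? One sentence would settle it.

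**Future studies only.** Give the same survey just before the first spray and count symptoms that are new or worse afterwards. This takes a few minutes per participant and may prime later reports. The past tense and the observed heart rates suggest that data collection here is complete, so it is not a remedy for this trial.
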